Appendix 4. Guidance on Reporting Nonserious Adverse Events for A4091065

This list provides general guidance on Sponsor expectations for non-serious adverse event reporting, which will focus on neurologic events that might be due to NGF inhibition. Adverse events of interest include the following:

- Congenital neurological abnormalities (eg, congenital nystagmus).
- Sympathetic nerve abnormalities (eg, bradycardia, syncope, decreased sweating).
- Sensory nerve abnormalities (eg, decreased sensation leading to abnormal number of falls, decreased pain sensation).
- Non-neurological adverse events that could be due to underlying neurologic dysfunction (eg, staring spells that may be indicative of infantile seizure, oculomotor tracking abnormalities).

If the investigator is unsure if an event is neurological in nature, it is recommended that the event is reported.

Investigators are also encouraged to report any non-serious AE that may be considered related to the infant's exposure to tanezumab.

1. VERSION HISTORY

This Statistical Analysis Plan (SAP) for study A4091065 is based on the protocol dated 26APR2016.

Table 1. Summary of Major Changes in SAP Amendments

SAP Version	Change	Rationale
1.0 (13OCT2016)	Not Applicable	Not Applicable
2.0	Section 7	Added the interim summaries for submission.
3.0	Section 6.6	Added to create listing about mother's exposure in parent studies as per team discussion.

2. INTRODUCTION

Note: in this document any text taken directly from the protocol is *italicised*.

This SAP provides the detailed methodology for summary and statistical analyses of the data collected in study A4091065. This document may modify the plans outlined in the protocol; however, any major modifications of the primary endpoint definition or its analysis will also be reflected in a protocol amendment.

2.1. Study Objectives

This study will examine post-natal neurologic and cognitive development of infants who were exposed to tanezumab or placebo or comparator in-utero during the tanezumab clinical program (through maternal participation in a tanezumab clinical study) within the following protocols: A4091056, A4091057, A4091058, A4091059, A4091061 and A4091063. The specific objective is:

- Evaluate physical development, neurological development (including the autonomic nervous system) and cognitive development through the age of 15 months of infants (and possibly beyond until the infant is considered stable in the judgment of the pediatric neurologist, developmental psychologist or pediatrician) exposed to tanezumab, placebo or comparator in-utero due to maternal participation in a tanezumab clinical study. All observed or volunteered SAEs and non-serious neurological or neuro-developmental adverse events regardless of treatment group or suspected causal relationship to the investigational product(s) will be reported.*

2.2. Study Design

This study is a multicenter, prospective, cohort study with enhanced physical and neurodevelopmental surveillance to characterize the outcomes related to the development of infants up to the age of 15 months, who were exposed to tanezumab, placebo or comparator

via maternal exposure at conception or in-utero in any tanezumab clinical study at any investigational site. The postnatal monitoring will include assessments at birth, (0-2 months), approximately 8 months and approximately 15 months of age up to a maximum of 36 months of age as needed.

This is an observational study, using enhanced surveillance of infants with potential exposure in-utero whose mother participated in a tanezumab clinical study. There is no active study treatment in this observational study. However, the neonatal/pediatric evaluations should be performed in a blinded fashion (while the mother of the infant is informed as to treatment allocation, the evaluator is not informed to the treatment the infant's mother received).

This study is designed to evaluate neurological and psychological development outcomes among infants with maternal exposure in-utero in tanezumab clinical studies. Because all tanezumab clinical studies exclude women who are currently pregnant and instruct female subjects of childbearing potential and at risk for pregnancy to use highly effective method(s) of contraception throughout the study and for 16 weeks after the last dose of subcutaneous investigational product, the total number of eligible subjects is expected to be small (fewer than 20). As such, there will not be sufficient statistical power to make use of formal statistical comparisons. Therefore, all analyses will be descriptive in nature, primarily through counts of observed outcomes.

Following is the schedule of assessments from the protocol:

Protocol Activity	Screen	0-2 Months	8 Months	15 Months/ET ^{c,d}
		Visit 1	Visit 2	Visit 3
Informed consent	X			
History & Physical Examination				
Occipital-frontal head circumference		X	X	X
Length		X	X	X
Weight		X	X	X
Vital Signs		X	X	X
Post-birth age (weeks)		X	X	X
Neurological Examination		X	X	X
Developmental Assessments	BINS ^a		X	X
	REEL-3 ^b		X	X

- a. Bayley Infant Neurodevelopmental Screener. (BINS).
- b. Bzoch-League Receptive Expressive Emergent Language Test, third edition (REEL-3).
- c. End of Treatment (ET)/Follow up visit: The need for further physical, neurological or developmental evaluations will be determined at the 15 month visit by the pediatrician, pediatric neurologist or a psychologist.
- d. Post-study subject interview (if applicable): The need for additional post-study follow up visits will be determined subsequent to the Visit 3 (15 month) visit and may extend to a maximum of 36 months as needed (eg, should a physical or neurodevelopmental delay be observed to be not within the range of normal development by the evaluating pediatrician, pediatric neurologist, or psychologist, an additional interview may be conducted up to 36 months of age).

3. ENDPOINTS AND BASELINE VARIABLES: DEFINITIONS AND CONVENTIONS

3.1. Primary Endpoint(s)

The specific endpoints for this study are:

- *Physical/safety measures (occipital-frontal head circumference, length, weight) and vital signs (blood pressure, pulse rate, respiratory rate, temperature).*
- *Neurological measures (mental status, cranial nerves, motor and sensory systems, reflexes).*
- *Psychological measures: Bayley Infant Neurodevelopmental Screener (BINS), Bzoch-League Receptive Expressive Emergent Language Test, third edition (REEL-3).*

The above measures will be used by the investigators to complete a maturation and development assessment CRF.

Descriptive assessments of the neurologists and psychologists may be incorporated into the Clinical Study Report on an individual basis.

3.2. Secondary Endpoint(s)

Endpoints are not distinguished as primary vs. secondary in the protocol. All are listed in the Primary Endpoint(s) section.

3.3. Other Endpoints

There are no other endpoints in this protocol.

3.4. Baseline Variables

Baseline variables are those collected at the initial visit.

3.5. Safety Endpoints

See [Section 3.1](#).

3.5.1. Adverse Events

All observed or volunteered SAEs and non-serious neurological or neuro-developmental AEs regardless of treatment group or suspected causal relationship to the investigational product(s) will be reported. Non-serious, non-neurological AEs will not be collected.

All AEs reported in the study will be summarized; there is no separate determination of 'treatment emergent' AEs because no study drug was directly administered to subjects in the study.

4. ANALYSIS SETS

4.1. Full Analysis Set

The primary analysis set for this study will be the Safety Population, defined as all subjects enrolled into the study. Subjects will be classified according to which treatment the mother was classified as receiving for safety analyses in the original tanezumab clinical study.

4.2. Per Protocol Analysis Set

No per protocol analysis set is defined for this study.

4.3. Safety Analysis Set

See [Section 4.1](#).

4.4. Other Analysis Sets

No other analysis sets are defined for this study.

5. GENERAL METHODOLOGY AND CONVENTIONS

The final summaries will be performed at study data set release after last subject last visit.

5.1. Hypotheses and Decision Rules

There are no statistical hypotheses or decision rules in this study.

5.2. General Methods

Results will be presented by the treatment group which the mother was classified as receiving for safety analyses in the original tanezumab clinical study.

Listings will include visit, visit date, calculated study day relative to date of birth and windowed study day. Windowed study days will be determined using windows as defined in [Appendix 1.1](#).

Vital signs data (including body length, head circumference and body weight) will be summarized descriptively by windows defined in 3 month intervals over the first 2 years and then 6 month intervals afterwards. Also these data will be summarized based on windows defined relative to target ages for comparison to normative data. No inferential statistical methods will be utilized. Study day windows are described in [Appendix 1.1](#).

5.3. Methods to Manage Missing Data

Summaries and listings will include only observed data. No imputation methodologies will be employed for missing data.

6. ANALYSES AND SUMMARIES

6.1. Primary Endpoint(s)

This study is designed to evaluate neurological safety related to both pregnancy outcomes as well as hypothetical risk of adverse development outcomes. However, the sample size...will

not be sufficient to generate more than a description of the safety outcomes outlined in the study endpoints. These results will be summarized as counts and associated rates of occurrence of each endpoint (stratified by randomized treatment arm from the original tanezumab clinical study the parent was identified through) as well as narrative descriptions of individual cases.

6.2. Secondary Endpoint(s)

There are no separate secondary endpoints.

6.3. Other Endpoint(s)

There are no separate other endpoints.

6.4. Subset Analyses

There are no planned subset analyses.

6.5. Baseline and Other Summaries and Analyses

Baseline data will be summarized.

6.6. Safety Summaries and Analyses

Standard safety reporting tables will list the safety data (including Adverse Events and Serious Adverse Events) as well as list patient demographics, disposition and summary status. A non-standard table will be produced listing parental characteristics to include the study, center, patient ID, and treatment group of the mother, and SAE report number associated with the pregnancy. Additional non-standard tables will list the outcome post delivery (newborn length, weight and head circumference) as well as investigator responses on the maturation and development assessment form.

In addition, a listing will be produced to evaluate exposure (days) from conception. The exposure is defined as

- ✓ the date from conception to last dose (injection) + 16 week for tanezumab, and
- ✓ the date from conception to the end of treatment for oral treatment group (tramadol).

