6.2. Study Period

The enrolled infants will participate from birth to at least the age of 15 months. The planned visits are outlined below. Neonatal/pediatric evaluations should be performed by a designated physician, such as a pediatric neurologist and a clinical psychologist (neurodevelopmental scales) who will be identified by the investigator or Pfizer.

6.2.1. (Visit 1) Newborn (0-2 Months of Age: Birth or at Any Time within 2 Months of Age)

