6.2.1.1. History and Physical Examination

Demographic data from the parents (obstetrics history, history of previous children) and estimated date of conception and gestational age at birth should be collected and recorded in a consultation report as provided by the obstetrician or gynecologist to the investigator as well as added to the CRF. Dosing dates with study drug are considered part of the initial protocol where the exposed mother participated but last maternal dosing date should be added to the current CRF.

Consultation reports and overall clinical impression of immediate pre-parturition maternal status provided by an obstetrician/gynecologist or practitioner are to be reported to the investigator. This information is to be maintained as a source document, a de-identified copy of which will be forwarded to the Sponsor within 35 days of receipt/completion.

Consultation reports and overall clinical impression from attending birth physician assessment of delivery difficulty: number/characterizations of any complications as minor or major reported to the investigator. This information is to be maintained as a source document, a de-identified copy of which will be forwarded to the Sponsor within 35 days of receipt/completion. Physical examination to include measurements of occipital-frontal head circumference, length, weight and post-birth age (weeks), and systolic and diastolic blood pressure, pulse rate, respiratory rate and temperature. The examiner will provide a report to the investigator.

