8. APPENDICES

Appendix 1. DATA DERIVATION DETAILS

Appendix 1.1. Definition and Use of Visit Windows in Reporting

Interval Based Study Windows

For the assessments made at study visits interval based study day windows are shown below. When multiple observations occur in a window, the observation closest to the window midpoint will be used, noting that the latter will be used in the case of a tie. If multiple observations occur in the last interval the last observation will be used.

Visit Window label	Window midpoint day	Study days
0-≤3 months	45	0 – 90
>3-≤6 months	135	91-180
>6-≤9 months	225	181-270
>9-≤12 months	315	271-360
>12-≤15 months	405	361-450
>15-≤18 months	495	451-540
>18-≤21 months	585	541-630
>21-≤24 months	675	631-720
>24-≤30 month	810	721-900
>30-≤36 months	[contact]
Etc...as needed		

Target Age Study Windows

To account for any early or late scheduled visits (compared to the target patient ages for normative data) we define ‘windows’ to be able to allocate each observation to a single specific study day window relative to date of birth. For the assessments made at study visits these study day windows are shown below. When multiple observations occur in a window, the observation closest to the target age will be used, noting that the latter will be used in the case of a tie.

Target Window label	Target Age	Study Days
0 – 2 months	<60 days	0-74
8 months	225 days	210-240
15 months	435	420-450

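### The first-window size summaries may mix birth size with up to two months of growth, with no age standardization and no defined age for the normative comparison

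*SAP*

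**What the plan says.** **Timing of the measurement.** Protocol 6.2.1 titles Visit 1 as the newborn visit and allows it at "Birth or at Any Time within 2 Months of Age". Protocol 6.2.1.1 has head circumference, length and weight measured there, with post-birth age in weeks. The Schedule of Activities has no earlier size measurement. The same section collects the estimated conception date and gestational age at birth.

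**Grouped summaries.** SAP 5.2 states: "Vital signs data (including body length, head circumference and body weight) will be summarized descriptively by windows" of 3 months over the first 2 years. A second set of windows, built around target ages, serves the comparison with normative data. Results are presented by the mother's treatment group. Neither SAP 5.2 nor Appendix 1.1 mentions standardizing size for postnatal or gestational age. SAP 3.4 takes baseline from the initial visit, so baseline size has the same spread of ages.

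**Windows.** In SAP Appendix 1.1 the first interval window is days 0-90 with midpoint 45. If an infant has several records in it, "the observation closest to the window midpoint will be used". The first target-age window is days 0-74, with a target of under 60 days; there, "the observation closest to the target age will be used".

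**Newborn table.** SAP 6.6 promises non-standard tables listing "newborn length, weight and head circumference" as the outcome after delivery. It does not say which record, visit or age supplies the values.

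**The concern.** Infants grow fast in the first two months, so an unstandardized length, weight or head circumference means little without the age at which it was taken. The later target windows respect this: each spans 31 days around an exact day. The earliest one is the widest and has no single target day.

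Three things are at stake. A first-window summary may combine birth values with values two months later. The comparison with normative data, which needs an age, has none defined in this window. And with so few infants, differences in age at visit will not reliably average out between treatment groups, so a reader may see a size difference that comes only from the calendar. In a purely descriptive study the summaries are the result, and SAP 7.2 allows interim summaries under this plan to enter a regulatory submission.

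**Working it through.** The plan calculates no sample size, power or error rate, so there is no figure of that kind to reproduce. The checks concern the windows and the effect of visit age.

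**1. Window arithmetic (SAP Appendix 1.1).**
- First interval window: (0 + 90)/2 = 45, as stated. The next eight stated midpoints are each within 0.5 day of (low + high)/2.
- 8-month target: (210 + 240)/2 = 225, with 240 - 210 + 1 = 31 days in the window.
- 15-month target: (420 + 450)/2 = 435, again 31 days.
- First target window: 74 - 0 + 1 = 75 days, and the target is a range.

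**2. Which record is kept.** Suppose an infant has records at day 0 and day 50. Their distances from day 45 are 45 and 5, so the interval rule keeps day 50 and drops the birth value. In the target-age window both records are under 60 days, and closeness to the target is undefined. If both count as on target, the SAP's tie rule takes the later one.

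**3. Chance difference in mean age between groups.**

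Inputs from the documents: Visit 1 timing of birth to 2 months (taken as 0-60 days); fewer than 20 infants in total (Protocol 9, SAP 2.2).

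Assumptions, because the documents give no figure: visit age uniform over W days with the same distribution in both groups; the group sizes shown; weight gain of 20-40 g/day.

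Formulas: SD of age = W/√12; SD of the difference in mean age = SD × √(1/n1 + 1/n2).

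For W = 60 and 5 vs 5: 60/√12 = 17.3 days; 17.3 × √(1/5 + 1/5) = 11.0 days. The median and 95th percentile of the absolute gap come from a simulation of 200,000 draws. The gram ranges multiply the unrounded gap by 20 and 40 g/day.

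| W (days) | Groups | SD of difference (days) | Median gap (days) | 95th percentile (days) | Median (g) | 95th percentile (g) |
|---|---|---|---|---|---|---|
| 60 | 3 vs 3 | 14.1 | 9.7 | 27.5 | 195-390 | 550-1,101 |
| 60 | 5 vs 5 | 11.0 | 7.5 | 21.4 | 150-300 | 427-855 |
| 60 | 9 vs 10 | 8.0 | 5.4 | 15.6 | 108-217 | 312-625 |
| 60 | 4 vs 15 | 9.7 | 6.7 | 19.0 | 134-269 | 379-758 |
| 74 | 5 vs 5 | 13.5 | 9.3 | 26.4 | 185-371 | 528-1,056 |
| 90 | 5 vs 5 | 16.4 | 11.2 | 32.1 | 224-447 | 641-1,282 |

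The rows for W = 60 assume visits within the protocol's limit. The rows for 74 and 90 show what the SAP windows would admit if visits ran late.

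**4. Extremes and expectation.** Two infants at opposite ends of 0-60 days differ by 60 × 20 = 1,200 g to 60 × 40 = 2,400 g. The expected gap between groups is zero when timing has the same distribution in both; the table describes chance variation around zero.

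**The case against.** The strongest reply is that a reader of the report can already see the ages. Post-birth age is recorded at every visit, SAP 5.2 puts study day from birth in the listings, and individual narratives are planned. There are no hypotheses and no inferential methods, and the plan says that the numbers cannot support comparisons. This stands for individual infants and is why the point is minor. It does not repair the grouped summaries or give the normative comparison an age.

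Four stronger readings are tempting, and the documents do not support them.

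- *Treatment groups will differ through visit timing.* Nothing shows that the timing of Visit 1 depends on treatment. Only a chance difference can be claimed.
- *A size difference would reflect age as much as exposure.* The documents give no exposure effect on size to set beside the age effect.
- *The SAP 6.6 table mislabels Visit 1 values as newborn.* The table is a listing, its source is not stated, and it is not tied to either set of windows. Even if Visit 1 is the source, the label follows the protocol's own title for that visit.
- *Birth size is missing from the data.* The delivery report in Protocol 6.2.1.1 is described by difficulty and complications, without mention of size. But Protocol 4 leaves pregnancy-outcome monitoring to the parent studies, SAP 6.6 links each infant to the report associated with the pregnancy, and the CRF is not part of these documents. The supportable statement is that the source is unspecified.

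**Conclusion.** The point holds for the first-window summaries in SAP 5.2 and Appendix 1.1. As written, they can pool unstandardized sizes taken up to about two months apart, or later if a late visit falls within day 74 or 90. The normative comparison has no defined age in that window, and its rule for choosing among records cannot be applied to a target that is a range.

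Under protocol-compliant timing and 5 vs 5 infants, the typical chance gap in mean weight is about 150-300 g, and one gap in twenty exceeds about 430-855 g. These figures rest on assumed uniform timing, assumed group sizes and an assumed 20-40 g/day. Larger groups give smaller gaps. The SAP says only that the data are summarized descriptively; I read this as unstandardized values because no standardization is named.

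For SAP 6.6 the defect is narrower: the source and age of the newborn values are not stated. This is a worthwhile, inexpensive improvement and does not threaten the study's descriptive purpose.

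**What to change.** **SAP 5.2 and Appendix 1.1.** Summarize length, weight and head circumference, and make the normative comparison, with age-standardized scores at each infant's exact age at measurement. Name the growth reference, and state how the gestational age already collected is used to correct for prematurity. These scores replace summaries of unstandardized values over days 0-74 or 0-90.

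**SAP 6.6.** State the source of the newborn values and list age at measurement beside each one. Use dated birth values where the delivery record holds them.

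**Cost.** Exact age comes from the study day that the SAP already calculates, so the main work is SAP wording and programming. A growth reference and a correction rule have to be chosen. Birth values may need CRF fields, since the protocol does not list size among the contents of the delivery report, and some values may be missing. Standardizing removes the part of a group difference that comes from age at measurement; ordinary variation between a few infants remains.

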7. INTERIM ANALYSES

7.1. Introduction

No interim analyses are planned for this study other than those done for the safety monitoring committee (SMC) and potentially for regulatory submission.

7.2. Interim Analyses and Summaries

The detail of interim analysis and summaries follows the SMC SAP.

Interim summaries of these data may be produced for inclusion in a regulatory submission. In this case, a snap-shot of the database will be taken and stored, then the data will be

summarized based on this analysis plan. If a clinical study that a mother participated in has not been unblinded at the time of a regulatory submission, the mother's treatment will be indicated as blinded.

8. APPENDICES

Appendix 1. DATA DERIVATION DETAILS

Appendix 1.1. Definition and Use of Visit Windows in Reporting

Interval Based Study Windows

For the assessments made at study visits interval based study day windows are shown below. When multiple observations occur in a window, the observation closest to the window midpoint will be used, noting that the latter will be used in the case of a tie. If multiple observations occur in the last interval the last observation will be used.

Visit Window label	Window midpoint day	Study days
0-≤3 months	45	0 – 90
>3-≤6 months	135	91-180
>6-≤9 months	225	181-270
>9-≤12 months	315	271-360
>12-≤15 months	405	361-450
>15-≤18 months	495	451-540
>18-≤21 months	585	541-630
>21-≤24 months	675	631-720
>24-≤30 month	810	721-900
>30-≤36 months	[contact]
Etc...as needed		

Target Age Study Windows

To account for any early or late scheduled visits (compared to the target patient ages for normative data) we define ‘windows’ to be able to allocate each observation to a single specific study day window relative to date of birth. For the assessments made at study visits these study day windows are shown below. When multiple observations occur in a window, the observation closest to the target age will be used, noting that the latter will be used in the case of a tie.

Target Window label	Target Age	Study Days
0 – 2 months	<60 days	0-74
8 months	225 days	210-240
15 months	435	420-450

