6.2.2.3. Developmental Assessment (Clinical Psychologist)

Developmental assessment (cognitive, social, language, gross and fine motor skills, neurological intactness) is recommended to be performed by a clinical psychologist utilizing the BINS and REEL-3. If a clinical psychologist is unavailable or cannot be readily located, the pediatrician or pediatric neurologist can perform the developmental assessments. The neonatal/pediatric evaluations should be performed in a blinded fashion (the evaluator is not informed to the treatment the infant's mother received).

Manuals for the collection of the BINS and REEL-3 will be provided to the parent protocol site and then forwarded to the relevant expert for data collection at the evaluation.

Consultation reports which describe outcome of each assessment and overall clinical impression from developmental assessment will be provided in a report to the investigator and entered in the CRF. This information is to be maintained as a source document, a de-identified copy of which will be forwarded to the Sponsor within 35 days of receipt/completion. The outcome of the clinical assessment by the psychologist will be reviewed by the investigator and overall clinical impression will be documented in the case report form.

6.2.3. (Visit 3) 15 Months of Age (Anytime during the 15th Month)

Assessments performed at Visit 2 will be repeated at Visit 3 to allow for evaluation of further development of cognitive function and the motor, sensory and autonomic functions.

The need for further neurologic or neurodevelopmental evaluations will be determined at the 15 month visit by the pediatric neurologist, developmental psychologist, or pediatrician and conveyed to the investigator. If there are no outstanding significant adverse events (AEs) present at the 15 month visit, participation in this current protocol will be considered

completed and additional follow up will not be required. See [Section 6.3](#) below for additional details if outstanding significant neurological or neuro-developmental AEs remain.

Submission of consultation reports and overall clinical impression to be submitted as previously described.

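### The SAP's 30-day months end the 15-month interval row at day 450, about a week before 15 calendar months, so some on-schedule Visit 3 growth and vital-sign data can fall into the next row and out of the target-age row

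*SAP*

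**What the plan says.** Protocol Section 6.2.3 schedules the last planned visit under the heading "15 Months of Age (Anytime during the 15th Month". The design text (Protocol Section 3, SAP Section 2.2) is looser: "approximately 8 months and approximately 15 months of age up to a maximum of 36 months of age as needed". Neither document turns this into a range of days.

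SAP Section 5.2 counts time as "calculated study day relative to date of birth" and plans two summaries of growth and vital signs. In the first, the data are "summarized descriptively by windows defined in 3 month intervals over the first 2 years", with 6-month intervals after that. The second is introduced as follows: "Also these data will be summarized based on windows defined relative to target ages for comparison to normative data".

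Appendix 1.1 gives the limits:
- Interval table: ">12-≤15 months" is days 361-450 (midpoint 405) and ">15-≤18 months" is days 451-540 (midpoint 495).
- Target-age table: the 15-month row is days 420-450 (target 435). No row follows it.

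If an infant has several measurements in one window, the interval table keeps the one nearest the midpoint and the target-age table the one nearest the target age. In a tie, the later one is kept. Section 5.3 uses observed data only.

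**The concern.** The two tables share an upper limit, day 450, that comes from counting every month as 30 days. Visits are likely to be booked from the birth date by the calendar, and 15 calendar months is several days longer than 450. An infant seen late in the permitted month would then be labelled older than 15 months in one table and dropped from the 15-month row of the other.

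Results are shown by the mother's treatment group, and fewer than 20 infants are expected in all. With so few, one or two infants displaced by a few days of scheduling can noticeably change a group's 15-month mean weight, length, head circumference or vital signs. The target-age row is also the one meant for comparison with norms, so a displaced infant leaves that comparison. SAP Section 7.2 allows these summaries to go into a regulatory submission.

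**Working it through.** **1. Reproduce the SAP's limits.** With a 30-day month, the upper edge is 30 × end month and the midpoint is 15 × (start month + end month).
- Row for months 12 to 15: edge 30 × 15 = 450; midpoint 15 × 27 = 405.
- Row for months 15 to 18: edge 30 × 18 = 540; midpoint 15 × 33 = 495.
- Target-age 15-month row: 30 × 14 = 420 to 30 × 15 = 450; centre 435.

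All nine legible interval rows and the 8- and 15-month target rows follow this rule. The tables are consistent with each other.

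**2. Place Visit 3 in calendar months.** The mean month is 365.25/12 = 30.4375 days. Birth is day 0, as in the first window.
- 14 months: 14 × 30.4375 = 426.1
- 15 months: 15 × 30.4375 = 456.6
- 16 months: 16 × 30.4375 = 487.0

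Counting actual dates for every birth date from 2016 to 2019 (years assumed, to cover a leap-year cycle), the day on which an infant turns 15 months is always between 454 and 458.

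**3. Compare the readings of the visit with day 450.**

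| Reading of Visit 3 | Days | Share after day 450 | Result |
|---|---|---|---|
| 15th month, 30-day months | 420-450 | 0% | one interval row; inside the target-age row |
| 15th calendar month (age 14 to under 15 months) | about 426-456 | 6/31 = 19% | split; the late part is outside the target-age row |
| Age 15 completed calendar months | about 454-488 | 100% | wholly in the later row; outside the target-age row |

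For the second reading, the date-by-date count gives a first day of 424-428, a last day of 453-457, and a share after day 450 of 18% on average (10% to 23% by birth date).

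**4. How often the second reading divides a group.** Assume visit days are uniform over the month, with p = 6/31. The chance that both rows are occupied is 1 − p^n − (1 − p)^n.
- n = 6 (an assumed group size): 1 − (6/31)^6 − (25/31)^6 = 0.73; expected number displaced 6 × 6/31 = 1.2.
- n = 19 (the largest cohort below 20): 0.98; expected number displaced 19 × 6/31 = 3.7.

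**5. The midpoint rule in the later row.** A Visit 3 on day 455 is 40 days from the midpoint of 495. A further measurement on days 456-534 is nearer, and one on day 535 ties and wins as the later. Such a measurement would replace Visit 3 in that row. Since day 455 is also outside days 420-450, that infant's Visit 3 values would then appear in the listings only.

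**The case against.** The best defence is that the SAP is coherent on its own terms. It uses 30-day months throughout, and on that convention the 15th month is exactly the target-age window. Day 450 then ends the visit and divides nothing. This stands: the table contains no arithmetic slip, and the problem depends on how sites read an undefined term.

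Some stronger inferences are tempting, and the documents do not support them:
- **That no row shows 15-month growth and vital signs.** The target-age table has such a row. What holds is that it also stops at day 450, with nothing after it.
- **That the visit is certainly split.** Only the calendar reading of the 15th month splits it. The 30-day and completed-months readings each keep it in one interval row.
- **That most visits are affected.** Allowing 14 days either side of 15 months (days 443-471) puts 21 of 29 days, or 72%, after day 450. No such tolerance is in the plan.
- **That planned follow-up routinely mixes into the later row.** Protocol Section 6.3 points to a visit about 6 months later. Adding 6 × 30.4375 = 183 days to days 426-456 gives about days 609-639, past day 540. Only an early or unplanned visit, which the protocol permits, would bring the midpoint rule into play.

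It is also fair to say that the consequence is modest. SAP Section 5.1 has no hypotheses or decision rules, narratives are planned, and the listings carry visit, visit date and study day, so a reader can reassemble Visit 3.

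**Conclusion.** The point holds conditionally. The day-450 limit is about a week short of 15 calendar months. If Visit 3 is booked in the 15th calendar month, about 18-19% of permitted days (10-23% by birth date) lie beyond it. Infants seen on those days are labelled ">15-≤18 months" and leave the target-age row, so neither summary then has a row holding the full Visit 3 cohort. On the completed-months reading the later interval row can hold the whole visit, but under a label beyond 15 months, and the target-age row loses it entirely. On the 30-day reading nothing goes wrong.

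The protocol heading accommodates more than one reading: 15 months of age suggests completed months, while the 15th month ends at that age. A window rule that works under only one reading should be corrected, but this is a tabulation weakness in a small descriptive study. It is not a loss of data or a threat to a test. The split probabilities in the working also assume uniform visit days and, for n = 6, an assumed group size.

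**What to change.** Preferred: summarise growth and vital signs by nominal Visit 1, 2 and 3, and list all other measurements by study day. This gives the full Visit 3 cohort one row under every reading. It means rewording SAP Section 5.2 and Appendix 1.1.

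Alternative: keep the age windows, but recompute every interval edge and midpoint with 30.4375-day months, and extend the target-age 15-month row to match. The edge at 15 months becomes day 456 or 457. Day 457 is the safer rounding, because the 15th calendar month ends on days 453-457 across all birth dates. This repairs the calendar reading only. Visits at 15 completed months would still fall almost wholly in the later row and outside the target-age row, so the SAP should also state in days what it takes the 15th month to mean.

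Do not simply replace the two rows around day 450 with one row of days 366-548. Beside the existing neighbours (271-360 and 541-630), that leaves days 361-365 unassigned and assigns days 541-548 twice.

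The cost is a SAP text change and the matching table programming. No new data, visits or procedures are needed.
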